## 2.2 SCHEMA

Total maximum n: 200; Total likely n: 120-160

Initial recruitment mailer (interested participants will contact the research team)

Pre-Screening  
<Day -20>

Pre-screen potential participants by inclusion and exclusion criteria  
Conduct informed consent process.

Visit 1  
<Time Point,  
e.g., Day 1>

Enroll; Randomize; Conduct baseline assessments

Arm 1  
N = 60

Arm 2  
N = 60

Visit 2  
<Day 90+/- 15>

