### 9.1 ENDPOINT AND OTHER NON-SAFETY ASSESSMENTS

Assessments for this study will include eligibility assessment and initial contact for pre-screening, as well as baseline and follow-up measures. We will also extract internal app data for the study period to assess adherence in the intervention arm (and to ensure no contamination in the control arm).

To ensure a focus on equitable representation and on a sample reflective of our interest in low income (publicly or non-insured) patients, the study team and health system research support staff determined that initial contact with recruiting materials (see above) will be prioritized to individuals seen at primary care clinics in the health system that see the largest proportions of publicly insured or non-insured patients. Iterative mailings will continue to prioritize patients from these clinics as well as patients in historically excluded and underrepresented groups (e.g., Black or Indigenous patients) among those fitting initial eligibility criteria (see above). Health system staff will conduct pre-screening procedures including identifying a potential sample and sending recruitment mailings (see Recruitment Collateral below). To ensure candidates are fully opted-in, GogyUp and study staff will not have access to any potential participants until participants contact GogyUp by filling out an online intake form or calling, texting, or emailing the GogyUp Research Coordinator through a study-designated phone number and email address listed on the recruitment letter.

Once eligible participants are consented by the GogyUp Research Coordinator, enrollment and baseline assessments will take place within an expected two-week (maximum) timeframe. Baseline assessments will include study staff administration (remotely via phone or video call) of the validated Health Literacy Questionnaire subscales 9 and 2, "Understanding health information" and "Having sufficient information," as well as the secondary outcome of the PDSMS. At three months post-baseline, study staff will conduct follow-up administration of the same outcomes. Based on our theoretical mechanism of action (see above), health literacy is the primary set of

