#### 10.4.2 ANALYSIS OF THE PRIMARY ENDPOINT(S)

We will specify the primary outcome as three-month follow-up level of the Health Literacy Questionnaire subscales 9 and 2 (understanding written information and having enough in enough information) as single endpoints (not repeated measures)..

We will compare the mean outcomes at follow-up between the treatment arms using analysis of covariance (ANCOVA), which compares follow-up outcome values between study arms while controlling for the baseline levels to gain power to detect an effect. The primary analysis will be an intent-to-treat (ITT); for non-monotonic missing (e.g., missing a baseline value), we will use multiple imputation with pattern mixture model adjustments in sensitivity analyses allowing for plausible differences among the missing—the justification for this is that pattern mixture models allow for a Missing Not At Random assumption, which is plausible in this case because we will not have measures for all likely variables associated with missingness. Pattern mixture models allow for us to set plausible values for missingness at both high or low levels to obtain a range of outcome estimates allowing for plausible missing data scenarios. For any monotonic missing—i.e., attrition (withdrawal or other lost to follow-up), we will use last observation carried forward but will also conduct sensitivity analyses using pattern mixture models under plausible assumptions of missing data patterns. We will present results using adjusted (least-squares) means with standard errors, p-values, and 95% confidence intervals. Baseline levels of endpoint outcomes will be included as a covariate to gain power to detect an effect, a standard use of ANCOVA.

---

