# RCT of Assistive-Reading Technology for Post-Visit Type 2 Diabetes Patient Education

Version 1.4

Protocol 1

10 February 2023

Step	Description	Documents & Scripts
3c	
Research Coordinator Calls Candidate
 
Candidate chooses this option by indicating their preference on the intake form accessed through gogyup.com/study.
 
Research Coordinator (RC) is notified via automation from JotForm and schedules the call, when possible, according to preferred time windows the candidate indicated on the intake form.
 
During the call, the RC will review and complete the Online Disclosure Document and Prescreening Form (Option 3a) with the Candidate. The candidate will receive a copy of the disclosure document and form responses via email which will also be automatically added to the candidate's database record.
 
If the candidate chooses to proceed, the call may continue to Step 4, 5, 6, and 7 with the option to switch to an online video session through Zoom.
	
Online Study Disclosure Document & Prescreening Form
 
Script:
 
 
• Step 3c: Intake Interview Script
 

3d	
Schedule Intake Call with Research Coordinator
 
Candidate chooses this option by selecting the Intake Call option on the intake form, choosing an open timeslot in the JotForm form and whether the call should be a tele- or videoconference.
 
As with Step 3c, the research coordinator will review the Online Disclosure Document and Pre-Screening Form with the Candidate in real time and the candidate will receive a copy of the form via email to review prior to the Consent Confirmation step.
 
If the candidate chooses to proceed, the call may continue to Step 4, 5, 6, and 7 with the option to switch to an online video session through Zoom.
	
Online Study Disclosure Document & Pre-Screening Form
 
Jotform Intake page
 
Scripts:
 
 
eMail opt-in confirmation
 
eMail opt-in
 

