4c	
Consent Signature
 
To gather the candidate's consent signature, the research coordinator launches a video conference in ZOOM, an accessible and HIPAA-compliant video / audio conferencing and screen sharing program and shares the conference link as well as a link to the online JotForm form to be signed.
	
Script: Step 4c – Consent Signature
 
Online Consent Form

5	
Enrollment & Assignment
 
The research coordinator verifies the participant's contact information and mailing address where the participant may securely receive packages.
 
The research coordinator then refers to the allocation sequence to determine intervention or comparison arm for the newly recruited participant.
 
Depending on the result, the participant is placed in the control or GogyUp Reader group.
 
If the participant is out of time, the RC schedules a baseline assessment with the participant prior to officially enrolling the participant.
	
Script: Step 5 - Enrollment & Assignment
 
Randomization Allocation Sequence

Step	Description	Documents & Scripts				

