##### 15.5.1.1 STEP 5A: ASSIGNMENT & NEXT STEPS

Thank the participant for enrolling in the study and explain the assignment process.

Review procedure detailed in section 6.3 of the study protocol to assign participant to a study arm: intervention or control.

*I am going to unseal this envelop that contains your assignment.*

Unseal the envelope and show the card to the camera so that the participant may view the assignment.

---

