15.5.1.4      STEP 5B: SCHEDULE FOLLOW-UP APPOINTMENT AND BASELINE ASSESSMENT

*The very last items we need to do is to set up an appointment to take a survey together to help establish some base line information.*

If there is enough time and the participant is willing, conduct the baseline assessment now. Otherwise, set up baseline and follow-up assessment appointments.

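### Participants see their arm before the self-rated baseline HLQ is taken, so the ANCOVA covariate is open to influence from the assignment; lock baseline first

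*Combined protocol and SAP*

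**What the plan says.** **Order of events.** The schema (2.2) lists "Enroll; Randomize; Conduct baseline assessments". The process list in 11.1.2 has assignment as step 5 and baseline as step 6. In the 11.1.4 workflow, step 5 reads "The research coordinator then refers to the allocation sequence to determine intervention or comparison arm for the newly recruited participant", and the HLQ follows at step 6. The script in 15.5.1.1 is explicit: "Unseal the envelope and show the card to the camera so that the participant may view the assignment". Sections 15.5.1.2 and 15.5.1.3 then have the arm spoken aloud. Only after that does 15.5.1.4 say: "If there is enough time and the participant is willing, conduct the baseline assessment now. Otherwise, set up baseline and follow-up assessment appointments".

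**Timing.** Steps 3c and 3d of the workflow allow everything in one sitting ("If the candidate chooses to proceed, the call may continue to Step 4, 5, 6, and 7"). Section 9.1 allows a gap: after consent, "enrollment and baseline assessments will take place within an expected two-week (maximum) timeframe". The Schedule of Activities (2.3) puts randomisation and outcome assessments on the same day without ordering them. No section requires the HLQ to come first.

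**Who knows the arm.** The research coordinator both assigns and administers the HLQ. The blinding in 7.3 covers investigators and analysis only.

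**Use of the baseline value.** Section 10.4.2 states "Baseline levels of endpoint outcomes will be included as a covariate to gain power to detect an effect". For attrition it states "we will use last observation carried forward". With a single follow-up visit, the carried-forward value is the baseline itself.

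**The concern.** ANCOVA is unbiased in a randomised trial because assignment cannot have affected the covariate. Here it can. A participant who has just learned that they get the app, or only paper, then rates their own ability to understand health information, and the person recording the answers also knows the arm. Raised app-arm ratings would make the adjusted analysis understate benefit. Lowered ones would make it overstate benefit.

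If baseline is deferred to a later appointment, three further problems follow:

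- **Mailing of control materials.** The control script (15.5.1.2) has them posted at assignment, arriving in 2 to 3 days. Sections 15.6 and 15.7 tie mailing to baseline. Under the first reading, a control participant could have study materials before the baseline HLQ.
- **Incentive to attend.** A $25 card that depends on completing baseline is offered only in the app arm (15.5.1.3, 15.6).
- **Loss after disclosure.** Someone who learns their arm and then misses baseline is marked as replaced once a new candidate attends (15.6.6), although the analysis population is as randomised (10.3).

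**Working it through.** **Inputs from section 10.2:** SD .74 for the Understanding subscale, SD .54 for Having sufficient information, 80 per arm, difference .3. Two-sided 5% tests come from 10.4.1.

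**Assumed, because the documents give no value:** the slope of follow-up on baseline, taken as .5 or .6 (equal to the correlation when both SDs are equal), and the shift b.

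**1. The plan's own power.** SE of an unadjusted difference = .74 × √(2/80) = .117. Then .3/.117 = 2.56, and Φ(2.56 − 1.96) = 72.7% (72.2% with the t distribution). The plan states 73%, so it reproduces. The 78% for 60 per arm at a difference of .37 also reproduces (78.2%).

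**2. ANCOVA with no shift.** SE = .74 × √(1 − slope²) × √(2/80) = .101 at slope .5 and .094 at slope .6. Power for .3 is 84% and 89%, and type I error is 5%.

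**3. Shift b in one arm, gone by follow-up.** Bias = −slope × b. For b = .10 this is .5 × .10 = .05 or .6 × .10 = .06 in size. Type I error = Φ(−1.96 + bias/SE) + Φ(−1.96 − bias/SE). Power when the shift opposes the effect = Φ((.3 − bias)/SE − 1.96). Each pair below is slope .5 / slope .6:

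| b | Size of bias | Type I error | Power for .3 |
|---|---|---|---|
| 0 | 0 | 5% | 84% / 89% |
| .05 | .025 / .03 | 5.7% / 6.2% | 77% / 82% |
| .10 | .05 / .06 | 7.8% / 9.8% | 69% / 73% |
| .15 | .075 / .09 | 11.5% / 16.1% | 60% / 61% |

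Simulation with 6,000 replicates agrees. For b = .10 it gives type I error of 7.3% / 9.8% and power of 69.5% / 72.1%. A wider range, slope .3 to .7 and b of .1 to .2 SD, gives bias of .022 to .104 and type I error of 5.5% to 23.6%.

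**4. Second primary subscale.** Shifts of .10 and .15 are .14 and .20 SD. On SD .54 that is .076 to .108. Multiplied by .5 to .6, the bias is .038 to .065.

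**5. LOCF with 20% random dropout, b = .10.** The carried-forward fifth raises the arm difference by .2b and the fitted slope to .8 × slope + .2. Bias is therefore −.8 × slope × b, or .04 to .048 in size. An unadjusted comparison that included LOCF values would be off by .2 × .10 = +.02.

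**6. Would the baseline table reveal it?** Section 10.4.5 plans a descriptive comparison only. Even a formal test would have power for a true .10 shift of Φ(.10/.117 − 1.96) plus a negligible second tail, about 14%. For .15 it is about 25%.

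**7. If a fraction p of the shift persists at follow-up.** Bias is (p − slope) × b in the current order and p × b with baseline first. At p = 1 and b = .10 that is +.05 / +.04 against +.10. Simulated type I error is 7.7% / 7.2% against 16.2% / 18.0%.

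**The case against.** The strongest objection is step 7. Participants know their arm at both assessments, so a reporting shift may persist. By the formula, the current order has the smaller absolute bias whenever p exceeds slope/2, that is 25 to 30% at the assumed slopes. The arithmetic stands, and the table in step 3 rests on p = 0. But the smaller figure comes from two reporting biases partly cancelling, by an amount nobody can know or report. The persistent part is the open-label outcome problem, which needs its own answer. It is no reason to keep an exposed covariate.

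It is also fair that the shift may be zero. The HLQ items are general and none mentions the app, and on the one-call path nothing has yet been received. Certainty attaches to the sequence, not to any effect on the estimate.

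Other replies carry less weight:

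- **Missing data.** Section 10.4.2 plans multiple imputation for a missing baseline and pattern-mixture sensitivity analyses, and 8.2 lets randomised people who do not receive the intervention be replaced. None of this says whether a replaced person stays in the as-randomised set, so 15.6.6 and 10.3 still need reconciling.
- **The $25 card.** It is described as an offset for network costs, for app-arm participants using their own device. It still depends on completing baseline and exists in one arm only.
- **Envelope versus sequence.** Envelopes can be prepared from a sequence. The mismatch between 15.5.1.1 and 7.3 with workflow step 5 is a wording conflict, not evidence that allocation was unconcealed.

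**Conclusion.** The concern holds. Every section that orders the two steps reveals the arm first, and the value collected afterwards enters the primary model as covariate and, under LOCF, as outcome. The size is not knowable from the documents: zero if disclosure does not move ratings, and otherwise slope × b in either direction. Under the stated assumptions (slope .5 to .6, SD .74, 80 per arm, shift gone by follow-up), shifts of .05 to .15 give bias of .025 to .09 and type I error of about 6 to 16%. If the shift opposes the effect, the power gained by adjusting is largely or wholly lost: at .10 power is back near the 72% of the unadjusted test, and at .15 it is below it. The planned descriptive table would probably not show shifts of this size. This should be fixed, because it is an avoidable weakness in the primary estimate and correcting it costs little.

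**What to change.** 1. Complete, time-stamp and lock the baseline HLQ, the demographics and the baseline Perceived Diabetes Self-Management Scale before randomising or revealing the arm. Section 9.1 requires that scale at baseline, but the baseline script (15.6.2) omits it. Edit 2.2, the list in 11.1.2, workflow steps 5 and 6, and 15.5 to 15.6 to match.
2. Randomise no one without a completed baseline, so that no randomised participant is replaced for missing it. Reconcile 15.6.6 with 10.3.
3. Reconcile 7.3 and workflow step 5 with the envelope in 15.5.1.1, so that each assignment is released singly after the baseline form is locked. Correct that script's pointer to section 6.3, which is Lifestyle Considerations.
4. Reconcile 15.5.1.2 with 15.6 and 15.7 on when control materials are mailed.
5. For anyone enrolled under the current order, record the assignment and baseline dates and report losses between them by arm. Add an unadjusted comparison of observed follow-up values as a sensitivity analysis, without LOCF values, because a shifted baseline would re-enter through them.

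The cost is a swap of two steps that can already fall in one call, the script and schema edits, one extra analysis, and IRB approval of the amendment before use (section 1). Participants who need a second appointment learn their arm a few days later. Sample size is unaffected. Unblinded self-report at follow-up remains and should be acknowledged separately.

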##### 15.5.1.2 STEP 5A-1: CONTROL GROUP ASSIGNMENT

If participant is assigned to the control group (content only), state:

*Oh, great! You are assigned to what we're calling "the control group" – this is the group that will use standard, printed diabetes education materials. I will send them to you in the postal mail and they should arrive in 2 – 3 days.*

Note assignment in candidate's JotForm record and send materials in the postal mail.

---

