**Note for Intervention Group Participants:**

- If participant is in Intervention group, explain that the data plan compensation or tablet will be sent once the baseline assessment has occurred.

*Ok – great! Next, we need to set up a time to meet for 10 – 15 minutes to take a survey together. If you have the time, we could do that now. Otherwise, what days and times would work with your schedule?*

*Again, thank you so much for joining the study. Over the next few months, always free to contact me if you have any questions about the study, how to access GogyUp Reader, etc..*

**IMPORTANT:** Assign the participant a study number and note the assignment in the candidate's record in the JotForm database and whether to follow up.

You will need the participant's study number for the GogyUp training.

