15.6 STEP 6: BASELINE ASSESSMENT AND PROCEDURES

**Notes:**

- A participant's ability to follow through and keep the baseline assessment appointment may indicate whether the participant will remain active or become inactive.
- For participants in the control group, education materials should be mailed once the baseline assessment is confirmed. Ideally, the follow-up appointment should be confirmed as well.
- For participants in either group who miss their baseline assessment appointment, at least three attempts (which can be a mix of voice call / voicemail and SMS messages) should be made to contact and reschedule.
- For participants in the intervention (GogyUp Reader) group, data plan reimbursement should be made available only after the baseline assessment has been completed and a follow-up appointment has been confirmed.
  - If a participant mentions they do not have internet access or an internet-enabled device, notify GogyUp's administrative assistant to provision a tablet for the participant.
- After the baseline assessment is complete, follow the script for onboarding participants in the intervention group.

---

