## 15.6.7 INTERVENTION GROUP – ONBOARDING FOR GOGYUP READER

After the baseline assessment is completed, display the quick start guide (see section 15.7.2) and ask if the participant is ready to try GogyUp Reader.

If the participant does not have the time or access to an internet-connected device, explain that they will receive a quick start guide with their network access reimbursement. If they would like help with accessing the app, they are always welcomed to contact the research coordinators.

If the participant is ready and available, walk through these steps.

- 1) Point to step 1 in the Quick Start Guide and point out that the GogyUp Reader can be used on any Android or iOS device – or on a PC with a Chrome or Edge web browser.
- 2) Ask the participant which device they plan to use and verify they are able to find the GogyUp Reader on their device's app store (or through their browser).
- 3) Point to step 2 and state that the next step is to fill out a GogyUp profile. This information is used to sync progress so that if they want to use GogyUp on another device, they can.
  - a. Note that they don't have to use their real name.
  - b. For the **UserName** they should use their assigned **Study Number**.
- 4) Point to step 3 in the Guide and note that if the participant has a preferred language other than english, they may select from the options to have an individual word translated into that preferred language.
- 5) Point to step 4 and emphasize that the participant should put in “**ninr1**” in the invite code box – this is needed so that the participant has access to the content library for the study.
- 6) Guide the participant to tap “Save profile” and then point out the different features in the app:
  - a. **Points A&B** in the Guide's Features section: Touch any word to launch the “word menu”
    - i. Request that the word be spoken, defined, or translated.
    - ii. Point out the “hear sentence” button if the participant wants the entire sentence spoken.
    - iii. Note that some words will have a “practice” button – this is a quick, optional spelling activity and isn't related to the study.
  - b. **Point C:** Demonstrate how the EZText button can instantly re-format the text so that it fits better on smaller screens and enables individuals to focus on individual words and phrases. Point out how the participant can increase the font size.

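### The assignment script has control materials mailed before a baseline that may be deferred, against the protocol's own baseline-first order

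*Combined protocol and SAP*

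**What the plan says.** **Control arm at assignment (15.5.1.2).** The coordinator tells the participant about the printed materials: "I will send them to you in the postal mail and they should arrive in" two to three days. The staff instruction that follows is to note the assignment in the participant's "record and send materials in the postal mail". Neither sentence mentions the baseline.

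**Baseline timing (15.5.1.4, 9.1).** The baseline comes after assignment in the script. It is done in the same call if time allows. "Otherwise, set up baseline and follow-up assessment appointments" is the alternative. Section 9.1 gives up to two weeks after consent for enrollment and baseline.

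**Control arm in the baseline notes (15.6).** For controls, "education materials should be mailed once the baseline assessment is confirmed". The next sentence reads "Ideally, the follow-up appointment should be confirmed as well".

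**App arm.** In the same notes, "data plan reimbursement should be made available only after the baseline assessment has been completed". In 15.5.1.4 the coordinator is told to "explain that the data plan compensation or tablet will be sent once the baseline assessment has occurred". Onboarding in 15.6.7 begins "After the baseline assessment is completed, display the quick start guide", and it is there that the participant receives the invite code for the study library.

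**General order.** The numbered steps in 11.1.2 put baseline assessment sixth and provisioning seventh, whichever route the candidate takes. Section 15.7 places provisioning of both arms after a completed baseline.

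**Use of the baseline score (10.4.2).** Each primary endpoint is compared by ANCOVA adjusted for its baseline level. Attrition is handled by last observation carried forward (LOCF), with pattern mixture sensitivity analyses.

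**Frequency.** Workflow Step 7 in 11.1.4 has control packets going out weekly. Sections 15.7 and 15.7.4 describe one set, enclosed with the welcome letter, to be read over 12 weeks.

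**The concern.** ANCOVA on a baseline score relies on that score being unaffected by treatment. Randomization balances what exists before allocation. It does not protect a covariate measured after one arm has received its materials and the other has not. The HLQ items include self-ratings of whether the respondent has enough health information, so receiving a set of diabetes fact sheets could plausibly change the answers. The same score is the carried-forward outcome for anyone lost to follow-up.

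The text at fault is a script that coordinators read and act on during the call. The app-arm scripts carry an explicit baseline condition and the control script at assignment does not, so any early exposure would fall on controls only.

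Separately, a report has to say what the comparator received, and the plan gives two accounts of how often materials were sent.

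**Working it through.** The plan gives no figure on this point. Its power figures in 10.2 reproduce and are not affected. With a two-sided 5% level and SD 0.74, power is Φ(difference / (SD × √(2/n)) − 1.96):
- 60 per arm, difference 0.37: Φ(2.739 − 1.96) = 78.2%, stated as 78%.
- 80 per arm, difference 0.30: Φ(2.564 − 1.96) = 72.7%, stated as 73%.

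**Step 1: when may materials be released?**
- Control, 15.5.1.2: at assignment, with no baseline condition.
- Control, 15.6: when the baseline is *confirmed*. This could mean the appointment is confirmed or the assessment is done.
- Control, 15.7 and the 11.1.2 order: after the baseline.
- App arm, 15.5.1.3, 15.5.1.4, 15.6 and 15.6.7: after the baseline, in every place where a time is given.

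Only 15.5.1.2 clearly permits mailing before baseline, and only for controls.

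**Step 2: how long could the exposure be?** Assume assignment and mailing on the day of consent and a baseline on day 14, the limit in 9.1. With delivery in 2 to 3 days, materials are in hand for 14 − 3 = 11 to 14 − 2 = 12 days before baseline. This is a worst case. If the baseline is done in the assignment call, exposure is zero. If it is done before the post arrives, exposure is also zero.

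**Step 3: what would it do to the estimate?** Write b for the baseline-to-follow-up slope.

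Estimate = (follow-up mean, app − control) − b × (baseline mean, app − control).

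If early reading changes the control baseline mean by d and leaves follow-up scores unchanged, the estimate moves by +b × d. With positive b, that is toward the app if reading raises self-ratings, and against it if reading makes participants rate themselves lower.

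LOCF adds an opposing term. Suppose a share m of controls is lost to follow-up, with the same average change d, and hold b fixed. The control follow-up mean then also moves by m × d, and the net shift is b × d − m × d = (b − m) × d.

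The documents give none of d, b or m, nor the share of baselines that will be deferred. Neither the size nor the sign can be worked out.

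**The case against.** The strongest reply is that the governing order is clear. Section 11.1.2 says every candidate follows the same steps, with baseline before provisioning, and the workflow table and 15.7 repeat it. In 15.6.5 the coordinator checks the control participant's mailing address at the end of the baseline session, which presupposes that nothing has yet been posted. On this view 15.5.1.2 is a slip that a trained coordinator would not act on. The evidence of intent stands. It does not cancel a direct instruction in the script used at the moment of assignment, and it shows that the repair is only to align that script with the rest.

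It is also fair to say that 15.6 is not a separate third rule. The follow-up appointment is normally confirmed during the baseline session, so *confirmed* there can mean that the session has taken place. The word is ambiguous, and no more than that is claimed.

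A reader might infer that any missed baseline appointment opens the exposure window, because 15.6.6 spaces its contact attempts two days apart. That sequence describes people who do not respond and are then marked inactive. Someone who answers the first message may be rebooked at once. It does not show exposure among participants who supply a baseline score.

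A reader might also take weekly packets to mean many times more material. Workflow Step 7 gives no number of weeks, and the 17 fact sheets in 15.10 could be sent in instalments as one set. The conflict is about what was sent when, and no count of mailings follows from it.

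**Conclusion.** The point holds as a conflict between a working script and the protocol's own sequence. As written, 15.5.1.2 allows controls, and only controls, to have study materials before the baseline HLQ score is taken. Exposure needs three things: a deferred baseline, a coordinator who follows 15.5.1.2 over 11.1.2 and 15.7, and a participant who reads the packet first. The documents give no frequency for any of them. The worst-case window is 11 to 12 days, on the assumptions of same-day assignment and mailing and a day-14 baseline.

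A reader might go further and conclude that the primary comparison is biased toward the app or that its type I error is inflated. The documents do not support that. Any such figure would rest on invented values for the share exposed, the effect of the fact sheets on HLQ scores and the slope, and even the sign is open. Nor do they support saying that the design itself puts control materials before baseline.

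This is a modest correction, worth making because it protects the covariate of both primary analyses at little cost. The mailing-frequency conflict is secondary and concerns how the comparator is described.

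**What to change.** - **15.5.1.2:** delete the instruction to send materials at assignment, and make the two-to-three-day delivery promise run from completion of the baseline.
- **15.6:** for controls, replace *confirmed* with *completed*, so that in both arms study materials are released only after the baseline questionnaire is completed.
- **11.1.4, workflow Step 7:** change weekly packets to the single mailing in 15.7 and 15.7.4. If weekly mailing is what is actually done, say so in all three places.

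The cost is a wording amendment with IRB approval, and mailing a few days later for controls whose baseline is deferred. No new visits, data or analyses are needed.
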